9.4.5. Safety Monitoring

Lilly will periodically review evolving aggregate safety data within the study by appropriate methods. The study team will review safety reports in a blinded fashion according to the schedule provided in the Trial-Level Safety Review plan. Lilly will also review SAEs within time frames mandated by company procedures. The Lilly CRP will, as appropriate, consult with the functionally independent Global Patient Safety therapeutic area physician or clinical scientist.

9.4.5.1. Hepatic Safety Monitoring

If a study patient experiences elevated ALT ≥ 3 X ULN, ALP ≥ 2 X ULN, or elevated TBL ≥ 2 X ULN, liver testing (Appendix 4) should be repeated within 3 to 5 days including ALT, AST, ALP, TBL, direct bilirubin, gamma-glutamyl transferase, and creatine kinase to confirm the abnormality and to determine if it is increasing or decreasing. If the abnormality persists or worsens, clinical and laboratory monitoring should be initiated by the investigator and in consultation with the study medical monitor. Monitoring of ALT, AST, TBL, and ALP should continue until levels normalize or return to approximate baseline levels.

Hepatic Safety Data Collection

Additional safety data should be collected via the eCRF if 1 or more of the following conditions occur:

- Elevation of serum ALT to ≥ 5 X ULN on 2 or more consecutive blood tests
- Elevation of serum TBL to ≥ 2 X ULN (except for cases of known Gilbert's syndrome)
- Elevation of serum ALP to ≥ 2 X ULN on 2 or more consecutive blood tests
- Patient discontinued from treatment due to a hepatic event or abnormality of liver tests

- Hepatic event considered to be an SAE

9.5. Pharmacokinetics

Pharmacokinetic samples will be collected from all patients. Plasma tirzepatide concentrations will be determined from blood samples obtained from patients receiving tirzepatide treatment. Blood samples for PK assessment will be collected at Week 0, 7, 15, 23, and 40 of study drug treatment per the Study Schedule or at ET (see Section 2).

All patients will have a single PK sample collected following the first dose at Week 0. This PK sample can be collected any time after this first dose on the day of drug administration.

Additionally, each patient will be assigned via IWRS to one of the sampling PK time windows of 1 to 24 hours, 24 to 96 hours, or 120 to 168 hours post dose at Weeks 7, 15, and 23 of study drug treatment per the Study Schedule or at ET (see Section 2). The PK sample after the last dose of study drug administered at Week 39 will be collected at Visit 14 (Week 40).

The date and time of the most recent SC injection administered prior to collecting the sample must be recorded on the eCRF from the study diaries. The actual date and time at which each sample was drawn must be recorded on the laboratory requisition form. Instructions for the collection and handling of blood samples will be provided by the sponsor.

Concentrations of tirzepatide will be assayed using a validated liquid chromatography mass spectrometry method. Bioanalytical samples collected to measure tirzepatide concentrations will be retained for a maximum of 1 year following last patient visit for the study.

Drug concentration information that would unblind the study will not be reported to investigative sites or blinded personnel (until the study has been unblinded).

9.6. Pharmacodynamics

Samples to assess the PD properties of tirzepatide are included in the efficacy measures and not applicable in this section.

9.7. Pharmacogenomics

9.7.1. Whole Blood Sample(s) for Pharmacogenetic Research

A whole blood sample will be collected for pharmacogenetic analysis as specified in the Schedule of Activities (Section 2) where local regulations allow.

Samples will not be used to conduct unspecified disease or population genetic research either now or in the future. Samples will be used to investigate variable response to tirzepatide and to investigate genetic variants thought to play a role in T2DM. Assessment of variable response may include evaluation of AEs or differences in efficacy.

All samples will be coded with the patient number. These samples and any data generated can be linked back to the patient only by the investigator site personnel.

Samples will be retained at a facility selected by Lilly or its designee for a maximum of 15 years after the last patient visit for the study or for a shorter period if local regulations and/or ERBs/IRBs impose shorter time limits. This retention period enables use of new technologies, response to regulatory questions, and investigation of variable response that may not be observed until later in the development of tirzepatide or after tirzepatide become(s) commercially available.

Molecular technologies are expected to improve during the 15-year storage period and therefore cannot be specifically named. However, existing approaches include whole genome or exome sequencing, genome-wide association studies, and candidate gene studies. Regardless of technology utilized, genotyping data generated will be used only for the specific research scope described in this section.

9.8. Biomarkers

Biomarker research is performed to address questions of relevance to drug disposition, target engagement, PD, mechanism of action, variability of patient response (including safety), and clinical outcome. Sample collection is incorporated into clinical studies to enable examination of these questions through measurement of biomolecules, including DNA, RNA, proteins, lipids, and other cellular elements.

Serum and plasma samples for biomarker research will be collected at the times specified in the Schedule of Activities (Section 2) where local regulations allow.

Samples will be used for research on the drug target, disease process, variable response to tirzepatide, pathways associated with T2DM, mechanism of action of tirzepatide, and/or research method or in validating diagnostic tools or assay(s) related to T2DM.

All samples will be coded with the patient number. These samples and any data generated can be linked back to the patient only by the investigator site personnel.

Samples will be retained at a facility selected by Lilly or its designee for a maximum 15 years after the last patient visit for the study or for a shorter period if local regulations and ERBs impose shorter time limits. This retention period enables use of new technologies, response to regulatory questions, and investigation of variable response that may not be observed until later in the course of the development and commercialization of both study drugs.

9.9. Health Economics

The following questionnaires will be completed by the patients at specific clinic visits according to the Schedule of Events (Section 2). At these visits, the questionnaires should be completed before the patient has discussed their medical condition or progress in the study with the investigator and/or site staff and before any other study procedures if the patient is not adversely affected by their fasting condition.

9.9.1. Impact of Weight on Self-Perception Questionnaire

The IW-SP questionnaire contains 3 items that assess how often the patients' body weight affects how happy they are with their appearance and how often they feel self-conscious when out in public (Hayes and DeLozier 2015). Each item is rated on a 5-point scale ranging from "always" to "never." Total scores for the IW-SP are derived by summing the item scores and dividing by the number of items. The score can also be transformed to a range from 0 to 100. Higher IW-SP scores correspond to better self-perception (Hayes and DeLozier 2015).

9.9.2. Ability to Perform Physical Activities of Daily Living

The APPADL questionnaire contains 7 items that assess how difficult it is for patients to engage in certain activities considered to be integral to normal daily life, such as walking, standing, and climbing stairs (Hayes et al. 2012). Items are scored on a 5-point numeric rating scale, where 5 = "not at all difficult" and 1 = "unable to do." A raw overall score is calculated by simply summing the scores of the 7 items, and a transformed overall score is obtained by linearly transforming the raw overall score to a 0 to 100 scale. A higher raw overall score and a higher transformed overall score are indicative of better ability to perform activities of daily living.

9.9.3. European Quality of Life

Generic health-related quality of life will be assessed using the EQ-5D-5L (EuroQoL Group 2015). The EQ-5D-5L is a standardized 5-item instrument for use as a measure of health outcome. It provides a simple descriptive profile and a single index value for health status that can be used in the clinical and economic evaluation of health care as well as population health surveys. The EQ-5D-5L comprises 5 dimensions of health (mobility, self-care, usual activities, pain/discomfort, and anxiety/depression). The 5L version, introduced in 2005, scores each dimension at 5 levels (no problems, slight problems, moderate problems, severe problems, and unable to perform/extreme problems), for a total of 3125 possible health states. In addition to the health profile, a single health state index value can be derived based on a formula that attaches weights to each of the levels in each dimension. This index value ranges between less than 0 (where 0 is a health state equivalent to death; negative values are valued as worse than dead) and 1 (perfect health). In addition, the EQ Visual Analog Scale records the respondent's self-rated health status on a vertical graduated (0 to 100) visual analog scale. In conjunction with the health state data, it provides a composite picture of the respondent's health status.

The EQ-5D-5L is used worldwide and is available in more than 120 different languages. Details on the instrument, and scoring, organizing, and presenting the data collected can be found in the EQ-5D-5L User Guide (EuroQoL Group 2015).

10. Statistical Considerations

10.1. Sample Size Determination

Patients will be randomized in a 1:1:1:1 ratio to tirzepatide 5 mg, 10 mg, 15 mg, or placebo.

The trial is powered to assess superiority of tirzepatide 5 mg, 10 mg, or 15 mg versus placebo in parallel relative to mean change from baseline in HbA1c at 40 weeks under the following assumptions:

- use of 2-sample t-test to compare treatment means utilizing HbA1c data collected before initiation of any rescue medication and premature treatment discontinuation;
- up to 25% patients in tirzepatide arms and up to 35% patients in placebo arm initiating any rescue medication or premature treatment discontinuation;
- at least 0.65% (placebo adjusted) mean reduction in HbA1c for the tirzepatide doses; and
- a common standard deviation (SD) of 1.1%.

On the basis of these assumptions, randomizing 472 patients using a 1:1:1:1 randomization ratio to tirzepatide 5 mg (118 patients), tirzepatide 10 mg (118 patients), tirzepatide 15 mg (118 patients), and placebo (118 patients) will provide at least 90% power to establish superiority for a tirzepatide dose compared to placebo at a 2-sided significance level of 0.017. Furthermore, this sample size will ensure at least 90% power for the HbA1c superiority evaluation utilizing all available HbA1c data at 40 weeks with missing data imputed with a conservative multiple imputation method (as described in the Efficacy Analyses [Section 10.3.3] below), provided that the mean reduction in HbA1c for the tirzepatide doses is at least 0.65% (placebo adjusted) and SD increases to no more than 1.3% due to the inclusion of data on rescue medications, inclusion of data after premature treatment discontinuation, and missing data imputation.

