7.8.2.3. Management of Patients with Severe, Persistent Hyperglycemia during the Treatment Period

Severe, persistent hyperglycemia will be collected during the trial to assess the risk of extreme imbalance in glycemic control.

Investigators will be trained on the application of criteria for deciding when and how to intervene with patients who do not reach glycemic targets. If any of the FBG values within 1 week for 2 consecutive weeks exceed the limits outlined below and no intercurrent cause of the hyperglycemia could be identified (investigators should first confirm that the patient is fully compliant with the assigned therapeutic regimen and that he or she does not have an acute condition causing severe hyperglycemia), rescue medication will be prescribed as an add-on to randomized treatment. Patients will continue to follow the protocol-specified visit schedule as described in Section 7.4.2.

- >270 mg/dL (>15.0 mmol/L) from baseline to Week 6 (4 values/week)
- >240 mg/dL (>13.3 mmol/L) from Week 6 to Week 12 (4 values/week)
- >200 mg/dL (>11.1 mmol/L) from Week 12 to end of trial (4 values/week)
OR
- HbA1c \geq 8.5% (\geq 69 mmol/mol) by and after Week 24

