Patients who stop the study drug permanently will receive another glucose-lowering intervention and will continue participating in the trial according to the protocol to collect all planned efficacy and safety measurements. The new glucose-lowering intervention will be recorded on the eCRF specified for collecting antihyperglycemic medications.

Patients discontinuing from the investigational product prematurely for any reason should complete adverse event and other follow-up procedures per Section 2 (Schedule of Activities), Section 9.2 (Adverse Events), and Section 9.4 (Safety) of this protocol.

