6.12.1.3. Methods for Multiple Imputations

For efficacy analysis relative to “treatment-regimen estimand,” missing HbA1c data at the 40-week visit will be imputed based on “retrieved dropouts,” defined as patients who had their HbA1c value measured at the 40-week visit in the same treatment arm who prematurely discontinued study drug. In cases where there are not enough retrieved dropouts to provide a reliable imputation model (i.e., at least 1 arm has <8 patients who discontinued study treatment early and have endpoint visit measurements, or the model implemented by the SAS program does not converge), an alternative multiple imputation method with reference to the placebo group (placebo multiple imputation) will be used. If value of the imputed HbA1c change from baseline is <-6.0% or >6.0%, that value will be set to -6.0% or 6.0%, respectively, to avoid unrealistic imputed values.

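### Should the power claim for the treatment-regimen (FDA) analysis use a smaller HbA1c difference than the on-treatment claim?

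*Protocol*

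**What the plan says.** Protocol 10.1 (Sample Size Determination) sets 118 patients per arm and makes two claims.

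- **On-treatment claim.** A two-sample t-test "utilizing HbA1c data collected before initiation of any rescue medication and premature treatment discontinuation", with a difference of at least 0.65%, a common SD of 1.1%, and "up to 25% patients in tirzepatide arms and up to 35% patients in placebo arm initiating any rescue medication or premature treatment discontinuation". Power is at least 90% for a dose against placebo "at a 2-sided significance level of 0.017".
- **All-data claim.** The same sample size gives at least 90% power for the analysis of all available Week-40 values, "with missing data imputed with a conservative multiple imputation method", provided that "the mean reduction in HbA1c for the tirzepatide doses is at least 0.65% (placebo adjusted) and SD increases to no more than 1.3" per cent. The SD increase is put down to three things: data on rescue, data after stopping drug, and imputation.

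Protocol 10.3.3.1 makes the treatment-regimen analysis primary for the FDA. On what happens after an event, Protocol 7.8.2.3 says "rescue medication will be prescribed as an add-on to randomized treatment", and Protocol 8.1.1 says "Patients who stop the study drug permanently will receive another glucose-lowering intervention". SAP 6.12.1.3 imputes from same-arm patients who stopped drug early but have a Week-40 value. If any arm has fewer than 8 such patients, or the model does not converge, "an alternative multiple imputation method with reference to the placebo group (placebo multiple imputation) will be used".

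**The concern.** The second claim lets post-event and imputed data affect the spread but not the mean. Several features suggest the mean could move too. Rescue is an added glucose-lowering drug. Patients who stop study drug receive another one. The assumed event ceiling is higher on placebo (35%) than on tirzepatide (25%). The protocol itself calls the imputation conservative, and the SAP fallback borrows from placebo. Each of these could narrow the gap between arms.

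Neither document gives a source for 0.65%, 1.1% or 1.3%, a Week-40 missing rate, or a split of the SD increase among its three causes. The Phase 2 background in Protocol 3.2 reports no effect size or SD. A reader therefore cannot tell whether 0.65% is a cautious floor for both estimands or an on-treatment value reused. If it is the latter and the treatment-regimen difference is smaller, the FDA primary analysis would have less than the advertised 90% power.

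**Working it through.** **Inputs (Protocol 10.1):** n = 118 per arm; difference 0.65%; SD 1.1% on treatment and up to 1.3% for all data; event ceilings 25% and 35%; two-sided alpha 0.017. Alpha is not restated for the second claim, so 0.017 is assumed there.

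**Formula.** Two-sample t-test, noncentral t: ncp = difference / (SD × √(1/n₁ + 1/n₂)); power = P(T > critical value), with n₁ + n₂ − 2 degrees of freedom.

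**Step 1: the plan's own figures.**

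- All data: ncp = 0.65 / (1.3 × √(2/118)) = 0.65 / 0.1692 = 3.84; critical value 2.404 on 234 df; power **92.4%**. With the SAP's 0.01667 it is 92.3%.
- On treatment: 118 × 0.75 = 88 and 118 × 0.65 = 76 (rounded down); SD 1.1; power **91.2%**.

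Both meet the stated lower bound of 90%.

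**Step 2: how much room there is for a smaller difference** (118 per arm, no covariate gain).

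| Difference | SD 1.3% | SD 1.2% | SD 1.1% |
|---|---|---|---|
| 0.65% | 92.4% | 96.0% | 98.3% |
| 0.6175% (5% smaller) | 89.2% | 93.8% | 97.1% |
| 0.585% (10% smaller) | 85.3% | 90.9% | 95.3% |
| 0.4875% (25% smaller) | 68.3% | 76.3% | 84.1% |

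The smallest difference with 90% power is 0.625% at SD 1.3%, 0.577% at SD 1.2% and 0.529% at SD 1.1%. So at the SD ceiling the room is 0.65 − 0.625 = 0.025%, or 4%. At a difference of 0.65%, 90% power holds up to an SD of 1.35%.

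Power depends only on the ratio of difference to SD. The plan's condition is a ratio of 0.65/1.3 = 0.50, which is also met by 0.60% at SD 1.2% or 0.55% at SD 1.1%. If the SD does not reach its ceiling, the unused part absorbs some loss of difference.

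**Step 3: the covariates left out of Step 2.** The planned model is an ANCOVA with baseline HbA1c, country and past oral medication (Protocol 10.3.3.1, SAP 6.12.1.2). Suppose 1.3% is an unadjusted SD and the correlation of baseline with change is r. Both are assumptions; the documents give no value. Residual SD = 1.3 × √(1 − r²).

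| Assumed r | Residual SD | Difference for 90% power | Room below 0.65% | Power at 0.585% |
|---|---|---|---|---|
| 0 | 1.30% | 0.625% | 4% | 85% |
| 0.2 | 1.27% | 0.612% | 6% | 87% |
| 0.3 | 1.24% | 0.596% | 8% | 89% |
| 0.4 | 1.19% | 0.572% | 12% | 91% |

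**Step 4: does the difference have to shrink?** A simple dilution model subtracts two terms from 0.65%: a share of effect lost by tirzepatide patients with events, and an HbA1c gain in placebo patients with events. It treats event patients as otherwise like the rest of their arm. The protocol's rules say they are not. Rescue is triggered by persistently high fasting glucose, or by HbA1c of 8.5% or more from Week 24 (Protocol 7.8.2.3). The on-treatment comparison thus drops placebo patients selected for poor control. Once rescued and counted again, their mean may lie above or below that of the other placebo patients, so the difference can narrow or widen. On the tirzepatide side, rescued patients stay on study drug and add another agent, and those who stop receive a replacement, which limits the loss. The documents supply no figure that fixes the net result.

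**The case for a change.** The best case for acting is that an openly stated condition is still an unsupported one. Protocol 10.1 says the sample size will ensure 90% power, which is stronger than its support. An imputation called conservative would be expected to affect the mean as well as the SD. The estimand is the FDA's primary one, and two or three sentences would close the gap.

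Part of this stands. The reason for using one difference in both claims is missing, and at SD 1.3% without covariate gain the slack is small. The rest does not lead to a change:

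- The all-data sentence states its own difference, worded as a minimum. Reading it as the on-treatment value carried over is an inference.
- The low powers combine a difference below the stated minimum with the SD at its stated maximum, and ignore the ANCOVA.
- Any power computed for the placebo-based fallback needs a missing rate that the documents do not give. If it starts from an SD of 1.3% and then adds imputation variance, it counts imputation twice, because the protocol says 1.3% already covers it. The fallback itself applies only if an arm has too few retrieved dropouts or the model fails to converge.

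**Conclusion.** No change is needed. The claim is conditional, the conditions are stated, and the figure is right under them: 92.4% against at least 90%. What is missing is a rationale for the inputs, not a correct number. Supplying it would alter no sample size, model, imputation rule, significance level or stated power. The difference and SD assumed in Protocol 10.1 play no part in the analyses set out in SAP 6.12.

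The sensitivity is worth knowing. At the SD ceiling, unadjusted, 90% power needs about 0.625%, and a difference of 0.585% would give 85%. With an assumed baseline correlation of 0.2 to 0.4, that 85% becomes 87% to 91%. These figures are per dose, assume alpha 0.017 for the second claim, and say nothing about whether the treatment-regimen difference is in fact smaller, which the documents leave open. If the sponsor wishes, one sentence could say that 0.65% is meant as a floor for both estimands, or give power at a smaller difference. That is optional.

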10.2. Populations for Analyses

For purposes of analysis, the following analysis sets are defined in [Table GPGK.4](#).

Table GPGK.4. Description of Analysis Population and Data Sets

Analysis Set	Description
Screened patients	All participants who sign informed consent
Randomized patients	All patients who are randomly assigned a treatment arm
modified intent-to-treat (mITT) population	All randomly assigned participants who are exposed to at least 1 dose of study drug. In the event of a treatment error, participants will be analyzed according to the treatment they were randomized.
Efficacy analysis set (EAS)	Data obtained during Study Period II from the mITT population, excluding data after initiating rescue antihyperglycemic medication or stopping study drug.
Full analysis set (FAS)	Data obtained during Study Period II from the mITT population, regardless of adherence to study drug or initiation of rescue antihyperglycemic medication
Safety analysis set (SS)	Data obtained during Study Period II or III from the mITT population, regardless of adherence to study drug or initiation of rescue antihyperglycemic medication.

10.3. Statistical Analyses

10.3.1. General Statistical Considerations

Statistical analysis of this study will be the responsibility of Lilly or its designee. Any change to the data analysis methods described in the protocol will require an amendment ONLY if it changes a principal feature of the protocol. Any other change to the data analysis methods described in the protocol, and the justification for making the change, will be described in the statistical analysis plan (SAP) or the clinical study report. Additional exploratory analyses of the data may be conducted as deemed appropriate.

Unless otherwise noted, all tests of treatment effects will be conducted at a 2-sided alpha level of 0.05, and the confidence interval will be calculated at 95%, 2-sided. In statistical summaries and analyses, patients will be analyzed as randomized.

There will be 2 estimands of interest in comparing efficacy of tirzepatide doses with placebo. First estimand, the “efficacy” estimand, represents efficacy prior to discontinuation of study drug without confounding effects of antihyperglycemic rescue therapy. Second estimand, the “treatment-regimen” estimand, represents the efficacy irrespective of adherence to study drug or initiation of rescue antidiabetic drugs.

The primary efficacy assessment, guided by the “efficacy” estimand, will be conducted using the efficacy analysis set (EAS). The primary efficacy assessment, guided by the “treatment-regimen” estimand, will be conducted using the full analysis set. As they are intended for different purposes, no multiplicity adjustments will be made for conducting 2 primary efficacy assessments relative to efficacy and treatment-regimen estimands.

Unless specified otherwise, safety assessments will be guided by an estimand comparing safety of tirzepatide doses with placebo irrespective of adherence to study drug or initiation of antihyperglycemic rescue therapy. Thus, safety analysis will be conducted using the safety analysis set (SS). Selected safety analyses may be conducted after excluding data on rescue therapy or data after starting another antihyperglycemic medication.

Summary statistics for continuous measures will include sample size, mean, SD, median, minimum, and maximum. The analysis model to make comparisons among treatment groups relative to continuous measurements assessed over time will be a mixed model for repeated measures (MMRM) with terms:

- treatment,
- visit,
- treatment-by-visit interaction,
- country,
- any past prior use (yes or no) of any oral antidiabetic medication,
- baseline HbA1c category [$\leq 8.5\% (\leq 69 \text{ mmol/mol})$ or $> 8.5\% (> 69 \text{ mmol/mol})$],
- and baseline measurement as a covariate.

For analyses with HbA1c, the baseline HbA1c category will not be included in the model. An unstructured covariance structure will model the relationship of within-patient errors.

The Kaplan-Meier method will be used for estimation of cumulative event-free survival rates over time, and cox proportional hazards regression analysis will be used to compare hazard rates among treatments.

Summary statistics for categorical measures (including categorized continuous measures) will include sample size, frequency, and percentages. Fisher's exact test will be used to examine the treatment difference in categorical outcomes. Logistic regression may be used to examine the treatment difference in binary efficacy outcomes. The negative binomial regression model will be used for the treatment comparison of discrete count measures if deemed appropriate.

Other statistical methods may be used, as appropriate, and details will be documented in the SAP.

